10.3. Vital Signs

Vital signs include oral temperature, pulse (bpm), systolic and diastolic blood pressure (mmHg), and respiration rate (breaths/minute). Note that systolic and diastolic blood pressure will be summarized with the other anthropometric parameters. Observed values and changes from baseline for vital signs will be summarized at each visit and time point, as well as for most extreme change from baseline.

10.4. Electrocardiogram (ECG)

Electrocardiogram (ECG) parameters include HR (bpm), PR (ms), QRS (ms), QT (ms), QTcF (ms), and RR interval (ms). Observed values and changes from baseline for ECG parameters will be summarized by treatment group at each visit and time point.

Investigator reported ECG result will be tabulated by visit and worst-case post-baseline. In addition, the shifts from baseline to each visit and worst-case post-baseline will be summarized. Worst case post-baseline will be based on the worst observed value on or after the treatment start date. Categories will include within normal limits, abnormal without clinical significance, and abnormal with clinical significance.

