- f. Screening serologies include HIV RNA, HBsAg, anti-HCV antibody, HCV RNA (reflex testing, if HCV antibody result at Screening is positive), and SARS-CoV-2 PCR test. The SARS-CoV-2 PCR test may be performed locally and must be performed within 30 days before Baseline (Day 1), other viral serology tests should be performed by the central laboratory. Subjects with chronic HCV infection and liver disease who were treated with anti-HCV therapy and achieved a sustained virologic response at least 2 years prior to Screening are not prevented from study participation.
- g. A blood sample for genomics pertaining to NASH will be collected at all sites unless forbidden by local regulations. If not collected at Baseline, this sample may be collected at any other time after the subject signs the separate consent for this sample. Provision of blood samples for genomic analysis is voluntary.
- h. Also see further information regarding anthropometric measurements in Section 12.1.6.
- i. Single 12-lead ECGs are to be performed at the times indicated and at any other time as clinically indicated. ECGs should be performed before any blood draws planned for the same time period.
- j. On Day 1, a single 12-lead ECG should be performed up to 2 hours before and 4 hours (-1 hour/+ 2 hours) after the first study drug dose.
- k. Vital signs include oral temperature, pulse, systolic/diastolic blood pressure, and respiration rate. Measurements are to be made after the subject has been resting in a supine position for a minimum of 5 minutes.
- l. Abbreviated, symptom-directed physical examinations will include at a minimum, examination of focused liver signs (e.g., jaundice, spider angioma, palmar erythema, hepatomegaly, splenomegaly, asterixis), skin, and extremities, and any other areas needed to address any complaints or concerns verbalized by the subject. If hand-foot symptoms/signs present at this visit or previous hand-foot symptoms/signs increases in severity to a Grade 2 or above, a dermatologist consult should be considered for further evaluation and treatment recommendations.

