12.1.3. Electrocardiograms

Single 12-lead ECGs are to be performed for all subjects.

On Day 1, ECGs are to be performed up to 2 hours before and 4 hours (-1 hour/+ 2 hours) after the first study drug dose [REDACTED]

For calculated ECG parameters, the following web site should be used:

<https://www.mdcalc.com/corrected-qt-interval-qtci#next-steps>

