7.5. Reference Dates

- Screening date is defined as the electronic case report form (eCRF) provided date on which a subject was screened for study entry.
- Randomization date is defined as the date on which the subject is randomized to study treatment.
- Treatment start date is defined as the date of first dose of study drug (also referred to as Day 1).
- Treatment end date is defined as the date of last dose of study drug.
- The calculation of age will use the informed consent date as its reference date.
- Safety data, such as AEs and laboratory assessments will use the treatment start date as a reference date to assign treatment emergence.
- Study day will be based on treatment start date as a reference date.

Reference day calculations will be defined as:

- date of interest – reference date + 1 when the date of interest \geq reference date.
- otherwise, date of interest – reference date.

For example, duration of treatment is defined as treatment end date – treatment start date + 1.

If either date is missing, reference date calculations will not be performed.

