7.6. Baseline and Post-Baseline Changes

Unless stated otherwise, baseline will be based on the last non-missing value collected prior to the start of study treatment based on the treatment start date and time, if applicable. Post-baseline values will be those collected after the treatment start date and time, if applicable.

Change from baseline is defined as: post-baseline value – baseline value.

Percentage change from baseline is defined as: $(\text{post-baseline value} - \text{baseline value})/\text{baseline value} \times 100\%$.

7.7. Handling Below Limit of Quantification (BLQ) or Lower Limit of Quantification (LLOQ) Values

Any parameters with values identified as $<x$, $\leq x$, $>x$, or $\geq x$ will be analyzed using the ‘x’ value (the analysis will ignore the $<$, \leq , $>$, or \geq symbol).

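### SAP 10.4 sets the worst-case post-baseline ECG by date only, so it conflicts with SAP 7.6 and, read literally, can return the Day 1 pre-dose (baseline) ECG as the worst post-baseline result

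*SAP*

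**What the plan says.** SAP 10.4 plans two kinds of ECG output. Numeric parameters are summarised as observed values and changes by visit and time point. The investigator's overall reading has three categories (normal, abnormal but not clinically significant, abnormal and clinically significant). It is tabulated by visit and as a worst case, and "the shifts from baseline to each visit and worst-case post-baseline will be summarized". The window for the worst case is: "Worst case post-baseline will be based on the worst observed value on or after the treatment start date".

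SAP 7.5 defines the treatment start date as the calendar day of the first dose, which is Day 1.

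The protocol schedules two ECGs on that day. Table 2, footnote j: "a single 12-lead ECG should be performed up to 2 hours before and 4 hours" (minus 1 to plus 2 hours) after the first dose. Section 12.1.3 agrees: "On Day 1, ECGs are to be performed up to 2 hours before and 4 hours" after it.

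SAP 7.6 defines baseline, unless stated otherwise, as "the last non-missing value collected prior to the start of study treatment". Its next sentence reads: "Post-baseline values will be those collected after the treatment start date and time, if applicable".

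**The concern.** When the Day 1 pre-dose ECG is done as scheduled, it is the baseline under SAP 7.6. It is also dated on the treatment start date, so the date-only window in SAP 10.4 admits it as a candidate for worst post-baseline. One record could then serve as both the baseline and the post-baseline result compared with it.

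SAP 10 plans no formal safety testing, so the ECG evidence is descriptive and the tables need to mean what their titles say. If the pre-dose ECG is admitted:

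- an abnormality seen only before any drug was given is reported as a post-baseline abnormality;
- a subject who was better than baseline on every ECG after dosing is shown as unchanged;
- a subject with no ECG after dosing still appears to have post-baseline data.

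**Working it through.** The documents state no figure to reproduce. The check is to place each ECG against the two rules, then work out which table cells can change.

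**Step 1. Which ECGs count as post-baseline**

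| ECG | SAP 10.4 (date only) | SAP 7.6 (date and time) |
|---|---|---|
| Screening | no | no |
| Day 1, up to 2 h before dose | **yes** | **no** |
| Day 1, about 4 h after dose | yes | yes |
| Later visits (Weeks 26 and 52 are the safety endpoints in Protocol 6.2.4) | yes | yes |

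The rules differ on one record, the Day 1 pre-dose ECG. If it is missing, the Screening ECG becomes the baseline, and the rules agree.

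**Step 2. Which results change**

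Let b be the baseline (pre-dose) category and w the worst category after dosing, with higher meaning worse. The date-and-time rule reports w. The date-only rule reports max(b, w).

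- If w > b, then max(b, w) = w. Every shift to a worse category is unchanged, including its destination category.
- If w = b, nothing changes.
- If w < b, then max(b, w) = b. The subject moves from improved to no change and is tabulated at the pre-dose category.
- If no post-dose ECG exists, the date-only rule reports b, where there should be no result.

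Only the last two cases are affected.

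**Step 3. Size**

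Among subjects with at least one post-dose ECG:

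excess in worst-case abnormal rate = P(abnormal pre-dose) × P(normal on all later ECGs, given abnormal pre-dose)

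The documents give neither probability, so all inputs here are assumptions:

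| Abnormal pre-dose | Of those, normal on all later ECGs | Excess (points) | Subjects, of 108 / of 54 |
|---|---|---|---|
| 10% | 10% | 0.10 × 0.10 = 1 | 1.1 / 0.5 |
| 20% | 25% | 0.20 × 0.25 = 5 | 5.4 / 2.7 |
| 30% | 50% | 0.30 × 0.50 = 15 | 16.2 / 8.1 |
| 40% | 50% | 0.40 × 0.50 = 20 | 21.6 / 10.8 |

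Under the date-and-time rule the excess is 0.

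**Step 4. The improvement cells**

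For illustration, assume three post-dose ECGs, independent readings, and category probabilities of 70%, 27% and 3% at each reading. The probability that the worst post-dose category is better than baseline is 0.27 × 0.70³ + 0.03 × 0.97³ = 0.0926 + 0.0274 = 12.0%. With 80%, 18% and 2% it is 0.18 × 0.80³ + 0.02 × 0.98³ = 0.0922 + 0.0188 = 11.1%. Under the date-only rule both are exactly 0, because max(b, w) cannot be below b. Independence is a simplification: if abnormal readings tend to persist within a subject, the true figure would be smaller.

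**The case against.** The strongest reply is that SAP 7.6 already settles the matter. Its post-baseline definition uses date and time, SAP 10.4 uses the same term, and the two can be read together: take post-baseline values as SAP 7.6 defines them, from Day 1 onward. On that reading, including the start date is needed to keep the 4-hour ECG. The proviso in SAP 7.6 that allows exceptions is attached to the baseline sentence, not to the post-baseline one. SAP 10.4 also separates time points elsewhere: "Observed values and changes from baseline for ECG parameters will be summarized by treatment group at each visit and time point".

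Much of this stands. A programmer who follows SAP 7.6 will not make the error, so what the documents show is a conflict, not a mistake already built into the outputs. But SAP 10.4 is the ECG-specific rule and states its own window, and neither section says which governs. SAP 7.5 also makes the treatment start date the reference for assigning treatment emergence to safety data, which gives some support to the date-only reading.

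Stronger readings that a reader might infer are not supported:

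- **Every subject with a pre-dose ECG is affected.** A result changes only if the pre-dose category is worse than every later one, or if there is no later ECG.
- **The shift table loses a drug effect.** Step 2 shows that every worsening is preserved. Only the marginal worst-case tabulation can draw the arms together, by adding pre-treatment abnormalities to both.
- **The improvement cells are always empty.** They are empty only for subjects whose Day 1 pre-dose ECG exists. Improvement also remains visible in the by-visit shifts.
- **The percentage points are an estimate for this trial.** They follow entirely from the assumed inputs.

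**Conclusion.** The conflict is real and minor. Read literally, SAP 10.4 admits the Day 1 pre-dose ECG to the worst-case post-baseline set, and SAP 7.6 excludes it. Two outputs for the investigator-reported category are exposed: the worst-case tabulation, where abnormal counts can be too high, and the improved and no-change cells of the baseline-to-worst-case shift table. Subjects without any post-dose ECG could also be counted as having post-baseline data. By-visit tables, numeric parameters including QTcF, and all efficacy analyses are unaffected, and the rule does not depend on treatment arm.

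The size cannot be taken from the documents. The range of 1 to 20 points per arm holds only for the assumed inputs (10–40% abnormal before dosing, 10–50% of those normal afterwards). The conflict itself needs none of those assumptions. It requires only that the Day 1 pre-dose ECG was done as scheduled.

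**What to change.** In SAP 10.4, replace the date-only window with ECGs obtained after the date and time of the first dose, in line with SAP 7.6. The pre-dose ECG then serves only as baseline, and the 4-hour Day 1 ECG stays in the worst case. Moving the window to start after the treatment start date would be wrong, because it would drop that 4-hour ECG. It is worth adding that a subject with no ECG after the first dose has no worst-case post-baseline result and, if a Day 1 clock time is missing, that the scheduled pre-dose or post-dose label decides.

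The cost is one SAP sentence and one programming condition. No extra data collection is planned, since the Day 1 ECGs are already scheduled relative to the dose. The edit belongs in the SAP version approved before unblinding (SAP 2). If that has passed, SAP 11 provides for describing the change in the clinical study report.

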10.5. Ophthalmologic Examinations

The proportion of subjects experiencing ophthalmologic abnormalities will be tabulated by visit and by treatment group. The clinical interpretation of the ophthalmologic examination will be tabulated as normal or abnormal. The worst-case post-baseline will also be summarized.

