- m. Baseline eye examinations may be performed at any time during the Screening period. Eye exams at Week 4, Week 8, Week 13, Week 26, Week 39, Week 52, Week 56 and/or Early Termination are required only if eye-related signs or symptoms are reported by the subject or observed by the investigator. If a subject experiences a treatment-emergent eye abnormality, an eye examination inclusive of slit lamp and near and far visual acuity testing should be performed by a qualified ophthalmologist or optometrist within 24 to 48 hours of event onset or on the next business day after symptom onset to evaluate the abnormality.
- n. Hematology and coagulation parameters include hemoglobin, MCV, MCHC, hematocrit, platelet count, RBC count, WBC count with differential, ANC, and PT, aPTT, INR, and fibrinogen. See also [Table 5](#).
- o. Liver aminotransferases include AST and ALT. Liver aminotransferases collected as part of the clinical chemistry panel for safety are also applicable for efficacy assessments.
- p. Fasting clinical chemistries include chloride, carbon dioxide, sodium, potassium, glucose, BUN, calcium, magnesium, creatinine, albumin, ALT, AST, ALP, GGT, total bilirubin, indirect and direct bilirubin, and total protein. CPK (total and fractionated) is to be reported at Screening and at Baseline. See also [Table 5](#).
- q. Urinalysis includes specific gravity, pH, blood, glucose, protein, ketones, and microscopic examination of sediment, if present. See also [Table 5](#).
- r. Subject contact to reliably assess medication use between visits is encouraged around Week 10, Week 17, Week 23, Week 30, Week 34, Week 43, and Week 47. See Section 9.7 for a list of accepted and excluded concomitant medications. If a subject receives a vaccine, including the COVID-19 vaccine, details regarding that vaccine should be recorded as a concomitant medication(s), including manufacturer, dose, and dates of each injection. Any vaccine-related reactions should be recorded as described in Section 12.2.
- s. The same biopsy samples will be used for histology analysis by the central study pathologist and by digital pathology.

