12.1.4. Eye Examinations

Eye examinations are to be performed for all subjects by a qualified ophthalmologist or optometrist.

Near and far visual acuity is to be assessed by an ophthalmologist or optometrist using standard measures (e.g., Early Treatment Diabetic Retinopathy Study or similar) in each eye. If the subject wears corrective lenses (e.g., glasses), then visual acuity is to be checked first with corrective lenses and then without correction. A best-corrected examination is not required.

A slit lamp examination (biomicroscopy), including examination of the eyelids, conjunctiva, cornea, anterior chamber, iris, and lens, is to be performed after completion of visual acuity testing for the determination of corneal health.

Eye exams at Week 4, Week 8, Week 13, Week 26, Week 39, Week 52, Week 56 and/or Early Termination are required only if eye-related signs or symptoms are reported by the subject or observed by the investigator.

If a subject experiences a treatment-emergent eye abnormality, an ophthalmologic examination should be performed by a qualified ophthalmologist or optometrist within 24 to 48 hours or on the next business day after symptom onset to evaluate the abnormality.

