13. STATISTICAL CONSIDERATIONS

13.1. Statistical General Considerations

This is a multi-center, randomized, double-blind, placebo-controlled, parallel-design study to evaluate the safety and efficacy of TVB-2640 compared with matching placebo in subjects with NASH.

For “change from Baseline” and “percent change from Baseline” calculations, “Baseline” refers to the last measurement obtained prior to the first administration of study drug. Study Day 1 is the first day of study treatment (TVB-2640 50 mg or placebo). Demographic data (including age, race, ethnicity, sex, height, and weight), medical history, prior treatments, pretreatment clinical characteristics, and other baseline characteristics will be summarized by treatment group and overall.

Descriptive statistics will be displayed by treatment group for all subjects with liver fibrosis stage F2-F3, for all subjects with liver fibrosis stage F1-F3, and for all subjects, as appropriate, to provide an overview of the study results. As appropriate, descriptive statistics will also be displayed by treatment group and by enrollment group. For categorical parameters, the number and percentage of subjects in each category will be presented in data summaries. The denominators for percentages will be based on the number of subjects (n) appropriate for analysis. Continuous variables will generally be summarized based on the following: n, mean, standard deviation, median, minimum, maximum, and standard error of the mean. Categorical data will be summarized using frequency tabulations (number and percentage of subjects).

Demographics and Baseline characteristics (medical histories, physical examinations, and concomitant medications) will be summarized using descriptive statistics for continuous variables and frequency distributions for discrete variables. Study subjects who discontinue the study along with reasons for discontinuation will be summarized and listed. Confidence intervals will be at the 90% and 95% levels. All statistical analyses will be performed using SAS v9.4.

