7. GENERAL DATA HANDLING CONSIDERATIONS

All analyses will be conducted using SAS software Version 9.4 or higher.

All data in the database will be presented in by-subject data listings. Unless otherwise stated, all listings will be sorted by treatment group, center ID, subject number, and assessment date and time, if available.

Unless stated otherwise, continuous data will be summarized by treatment group using descriptive statistics including number of subjects (n), mean, median, standard deviation (SD), first quartile (Q1), third quartile (Q3), minimum (min) value, maximum (max) value.

Unless stated otherwise, categorical data will be summarized by treatment group using counts and percentage based on the number of non-missing values. For selected summaries, the number of missing values will be presented as a separate category with no percentage, if one or more subjects have missing data. Counts of zero will be presented without percentages.

Descriptive statistics will be presented with the following numerical precision:

- Minimum and Maximum: same as the raw data collected
- Mean, Median, Q1, and Q3: one additional decimal place to that reported for Minimum and Maximum
- SD: two additional decimal places than the Minimum and Maximum
- Percentages: reported to one decimal place if percent is <100. If the value is 100, no decimal place will be reported.

Unless otherwise noted, statistical inference will be based on two-sided testing with a 5% significance level. Confidence intervals will be at the 90% and 95% levels.

P-values will be reported to four decimal places. If the value is below 0.0001 it will be noted as < 0.0001; if the value above 0.9999 it will be noted as > 0.9999.

All data up to the time of study completion/withdrawal from the study will be included in the analysis, regardless of duration of treatment.

Numbering for data displays will be based on [International Council for Harmonization \(ICH\) E3](#) whenever possible.

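### SAP 10.5 leaves post-baseline eye-abnormality percentages on a symptom-selected denominator that can differ between arms

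*SAP*

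**What the plan says.** SAP 10.5 plans two summaries of the eye examination. The first is by visit: "The proportion of subjects experiencing ophthalmologic abnormalities will be tabulated by visit and by treatment group". The second is across visits: "The worst-case post-baseline will also be summarized". The section states no denominator for either.

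The general rule is in SAP 7: "Unless stated otherwise, categorical data will be summarized by treatment group using counts and percentage based on the number of non-missing values". For selected summaries only, "the number of missing values will be presented as a separate category with no percentage"; SAP 7 does not say whether the eye table is one of them. SAP 10 bases all safety reporting on the Safety population. Protocol 13.1 offers only a general statement: "The denominators for percentages will be based on the number of subjects (n) appropriate for analysis".

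On who is examined, the Baseline examination is scheduled for everyone. Footnote m of the Schedule of Assessments (Protocol Synopsis, Table 2) says of its timing: "Baseline eye examinations may be performed at any time during the Screening period". For Weeks 4 to 56 and Early Termination, Protocol 12.1.4 says eye exams "are required only if eye-related signs or symptoms are reported by the subject or observed by the investigator", and footnote m gives the same rule. The safety endpoint lists in Protocol 6.2.4 and SAP 5.2 nevertheless promise eye-examination findings from every study visit.

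**The concern.** Taken together, these rules make the post-baseline denominator a subset formed after randomisation and selected by symptoms. If the drug causes eye symptoms, more treated subjects are examined. Numerator and denominator then rise together, and the percentage need not move. A reader who takes the table at its label would see the proportion of subjects with abnormalities, when it shows how often an examined, mostly symptomatic subject was abnormal.

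Eye effects are a specific safety interest in this trial. Protocol 8.3 lists visual symptoms among the events managed by stopping study drug. Protocol 5.2 reports dry eye in 8 of the 21 treated subjects in the China cohort. SAP 10.5 is the only planned summary of the examination itself.

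**Working it through.** The documents give no eye-abnormality rate and no expected number of examinations, so there is no planned figure to reproduce. The check combines the rules and then varies the unknown.

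**Which denominator applies.** SAP 10.5 is silent, so the SAP 7 default governs. The Safety population in SAP 10 fixes who is eligible for the table. It does not replace the rule that percentages use non-missing values. By visit, the denominator is subjects examined at that visit. For worst case, it is subjects with at least one post-baseline examination.

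**Inputs.** Planned arm sizes are 108 and 54 (SAP 4.3), all assumed dosed and, for by-visit use, all on study. The numbers examined and abnormal are assumptions.

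**Formulas.**
- Examined-only percentage = abnormal / examined.
- All-subject percentage = abnormal / N, where an unexamined subject counts as having no abnormality detected.
- Ratio of the first to the second = N / examined.

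**Ratio over a range.**
- TVB-2640, 5 examined: 108/5 = 21.6.
- TVB-2640, 41 examined: 108/41 = 2.6. The 41 borrows the China dry-eye rate: 8/21 = 38%, and 0.38 × 108 ≈ 41. That rate accumulated over 12 weeks, so it resembles a worst-case count more than a single-visit count.
- Placebo, 3 examined: 54/3 = 18.0.
- Placebo, 5 examined: 54/5 = 10.8.

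The factor differs between arms whenever the examined fractions differ.

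**Effect on the arm comparison (assumed counts, TVB-2640 vs placebo).**

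| Examined | Abnormal | Examined-only | All subjects |
|---|---|---|---|
| 11 vs 5 | 9 vs 4 | 81.8% vs 80.0% | 8.3% vs 7.4% |
| 41 vs 5 | 33 vs 4 | 80.5% vs 80.0% | 30.6% vs 7.4% |
| 22 vs 3 | 18 vs 3 | 81.8% vs 100% | 16.7% vs 5.6% |
| 108 vs 54 | 18 vs 3 | 16.7% vs 5.6% | 16.7% vs 5.6% |

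In the first row both arms are inflated by a similar factor and little is lost between arms. In the second, a fourfold difference (30.6/7.4) does not show. In the third, the direction changes. In the last, everyone is examined and the two denominators agree, which confirms that selective examination is the source of the distortion.

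**Comparison with Baseline.** Baseline covers all subjects, while later visits cover mainly those with signs or symptoms. The percentage abnormal can therefore jump after Baseline with no drug effect.

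**Which table receives the examinations.** A treatment-emergent eye abnormality is to be examined within 24 to 48 hours or on the next business day (Protocol 12.1.4), often between scheduled visits. SAP 7.9 summarises by nominal visit without windowing. It lets unscheduled data into extreme-value and any-time summaries, and eye examinations are not among the data types it allows to be moved to the nearest visit. Off-visit examinations may therefore reach only the worst-case summary, leaving the by-visit table sparser still.

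**The case against.** The strongest reply is that eye symptoms are reported elsewhere on a sound denominator. SAP 10.1 summarises eye-disorder TEAEs by preferred term in the Safety population and repeats this in the mITT population. SAP 7.2 adds subgroup summaries. Under Protocol 12.2 the symptoms that trigger an examination should themselves be recorded as adverse events. This stands, and it limits the harm. A reader might infer from SAP 10.5 that an eye signal would be hidden from the trial report; the documents do not support that.

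A reader might also infer that the percentages will be grossly inflated, or that the arm difference will reverse. Neither follows. The number examined is not given, and the illustrations above rest on assumed counts. SAP 7 requires counts beside percentages, so a tiny denominator would show, and no formal safety testing is planned.

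It can be added that the denominator is inferred from a general rule, and that the Protocol says examinations are required for signs or symptoms without forbidding others. Both are true. But SAP 7 applies unless something else is stated, and SAP 10.5 states nothing else. Extra examinations would shrink the distortion; they would remove it only if nearly everyone were examined.

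Finally, an all-subject denominator has its own bias, because abnormalities without symptoms in unexamined subjects are missed. That is correct. The figure is a lower bound and must be labelled as one.

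**Conclusion.** The point holds as a defect in a descriptive safety table. Followed as written, SAP 10.5 and SAP 7 produce post-baseline percentages, by visit and worst-case, that are shares of subjects examined. Because post-baseline examination is required only for signs or symptoms, that group is selected after randomisation and can differ by arm. The percentages are not the proportion of subjects with abnormalities, and they cannot be compared reliably between arms or with Baseline.

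The size cannot be fixed from the documents. Relative to an all-subject percentage it is N / examined: about 2.6-fold if 41 of 108 are examined and about 22-fold if 5 of 108 are. This assumes that all 108 are dosed and on study, and that unexamined subjects count as having no abnormality detected. The separate TEAE summaries keep the consequence moderate. The change is still worth making, because it costs little and concerns an organ system of known interest.

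**What to change.** In SAP 10.5, override the SAP 7 default:

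- By-visit tables: use Safety-population subjects on study at that visit as the denominator.
- Worst-case post-baseline: use the whole Safety population.
- In both, show the number examined and the number abnormal by arm.
- Label post-baseline results as symptom-triggered, and the percentage as a lower bound (abnormality detected).
- Refer to the eye-disorder TEAE tables for the comparison between arms.

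Separately, the endpoint wording that promises eye findings at every visit (Protocol 6.2.4, SAP 5.2) and the symptom-only examination rule (Protocol 12.1.4, footnote m) must be reconciled.

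The analysis change costs a few sentences in the SAP and a revised table shell, with no new data. Its small downside is that symptom-free abnormalities in unexamined subjects are not counted, which the label discloses.
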